7.2.2.1 Summaries of adverse events for public disclosure

For the disclosure of the results to EudraCT and ClinicalTrials.gov (and not for the purpose of the clinical study report), treatment-emergent (S)AEs will be summarized displaying, for each dose group, counts and percentages of subjects with at least one treatment-emergent event plus the number of events (counted exactly the number of times they occurred also within a subject) by SOC and individual PT. The summary table is presented in descending order according to the overall incidence (i.e., SOC and

individual PT within each SOC with the highest number of occurrences appears first). Equal frequency of different individual PTs is sorted in alphabetical order of the individual PT.

The following summaries will be prepared according to the guidelines stated above:

- Summary of treatment-emergent SAEs
- Summary of treatment-emergent SAEs judged to be treatment related by the investigator
- Summary of treatment-emergent SAEs with fatal outcome
- Summary of treatment-emergent SAEs with fatal outcome judged to be treatment related by the investigator
- Summary of non-serious AEs with an incidence of 5% or higher in any treatment group

7.3 Deaths

Date of death and primary cause will be recorded on the 'Death' eCRF page. A listing including all deaths recorded in the database will be provided.

A separate listing will be provided displaying all AEs leading to death, i.e., with outcome 'fatal'.

7.4 Laboratory

A central laboratory will be used for all protocol-mandated tests. Laboratory values analyzed by local laboratories will only be listed.

Laboratory test results will be converted into Standard International units by the laboratory. Values outside the laboratory normal ranges will be flagged as well.

7.4.1 Measurements

Laboratory test results will be transferred from the central laboratory and provided in the SDTM structure, together with corresponding reference ranges in original, conventional, and standardized units. Assessments are performed at Screening visit, Visit 2 Day 1 (if more than 7 days after screening), Visit 2 Day 3, Visit 3, and at unscheduled visits based on the judgment of the investigator.

The following variables are collected as per protocol:

Hematology

- Hemoglobin (g/L)
- Hematocrit (L/L)
- Erythrocytes ($10^{12}/L$)

- Leukocytes with differential counts ($10^9/L$)
- Platelets ($10^9/L$)

Clinical chemistry

- Alanine aminotransferase (ALT) (U/L)
- Aspartate aminotransferase (AST) (U/L)
- Alkaline phosphatase (AP) (U/L)
- Total and direct bilirubin ($\mu\text{mol}/L$)
- Creatinine ($\mu\text{mol}/L$)
- Sodium, potassium (mmol/L)

For women of childbearing potential, urine pregnancy tests are performed at Screening Visit, Visit 2 Day 1, and Visit 4 (EOS). A pregnancy will be reported as an SAE; the results of the pregnancy tests will not be included in the clinical database.

7.4.2 Variables

For parameters assessed as a continuous variable, the following variables will be defined:

- Baseline
- Value at each post-baseline visit
- Absolute change from baseline to each post-baseline visit
- Position against reference ranges based on normal ranges provided by the laboratory.
- Position against marked abnormality range based on ranges provided in [Appendix D](#).

7.4.3 Analysis

All laboratory values will be listed. Values from local laboratories will be flagged in data listings and not used in any analysis.

7.4.3.1 *Values over time*

For continuous laboratory variables, descriptive statistics will be provided for observed values as well as for change from baseline at each scheduled study visit.

7.4.3.2 *Individual subject changes*

Laboratory test results from both, scheduled and unscheduled visits will be used to determine the incidence of markedly abnormal test results. The date of the sample will determine the analysis period the test is assigned to.

The number of subjects with newly occurring or worsening markedly abnormal laboratory values will be displayed for the analysis sets shown in [Table 4](#) and the periods shown in [Table 7](#).

The definitions of marked abnormal lab values are shown in [Appendix D](#).

7.5 Vital signs, physical findings, and other observations related to safety

7.5.1 Vital signs

Vital signs will be collected in an eCRF. Systolic blood pressure (SBP) and diastolic blood pressure (DBP) and pulse rate (PR) assessed in supine position will be entered in mmHg. Height (cm) and weight (kg) will be assessed in subject wearing indoor clothing without shoes.

7.5.1.1 Measurements

Height (cm) will be assessed at Screening Visit.

Body weight will be assessed at Screening visit, Visit 2 Day 1, Visit 2 Day 3, Visit 3 and at unscheduled visits.

SBP, DBP, and PR will be assessed at Screening visit, Visit 2 Day 1, Visit 3 and at unscheduled visits. Further assessments will be conducted at pre-specified time points in Period 2, i.e., Visit 2 Day 1 and Visit 2 Day 3 as shown in [Table 9](#).

Table 9 Schedule vital signs monitoring in Period 2

Visit Day	Time point	Assessment Description
Visit 2 Day 2	0 h	Shortly before morning (AM) i.v. selexipag infusion
	25 min	During AM i.v. selexipag infusion, 25 min after infusion start
	87 min	Shortly before end of AM i.v. selexipag infusion
	4 h	Four hours after initiation of AM selexipag infusion
	6 h	Six hours after initiation of AM selexipag infusion
	8 h	Eight hours after initiation of AM selexipag infusion
	12 h	Before PM selexipag infusion, twelve hours after initiation of AM selexipag infusion
Visit 2 Day 3	0 h	Shortly before morning (AM) selexipag infusion
	25 min	During AM selexipag infusion, 25 min after infusion start
	87 min	Shortly before end of AM selexipag infusion
	4 h	Four hours after initiation of AM selexipag infusion
	6 h	Six hours after initiation of AM selexipag infusion
	8 h	Eight hours after initiation of AM selexipag infusion before oral administration of selexipag
	12 h	Before PM Uptravi intake, twelve hours after initiation of AM selexipag infusion

7.5.1.2 Variables

For vital signs parameters, the following variables will be defined:

- Baseline
- Value at each post-baseline visit
- Absolute change from baseline to each post-baseline visit
- Absolute change from pre-dose to each post-dose assessment.

For supine SBP (mmHg) and supine DBP (mmHg), the presence of post-baseline abnormalities is derived according to the criteria defined in [Table 10](#) below:

Table 10 **Marked abnormalities in blood pressure**

Analysis Parameter	LL	L	Normal	H	HH
Supine SBP (mmHg)	-	SBP < 90	90 ≤ SBP < 140	140 ≤ SBP ≤ 159	SBP ≥ 160
	-	Decrease > 40 from baseline	-	Increase > 20 from baseline	-
Supine DBP (mmHg)	-	DBP < 50	50 ≤ DBP < 90	90 ≤ DBP ≤ 99	DBP ≥ 100
	-	Decrease > 20 from baseline	-	Increase > 20 from baseline	-

DBP = diastolic blood pressure; SBP = systolic blood pressure.

Abnormalities will be flagged for each post-baseline assessment individually and overall for the study treatment period.

7.5.1.3 Analysis

Values over time

A listing of all vital sign parameters will be created displaying all values in the database regardless if from scheduled or unscheduled visits. Marked abnormal values will be flagged.

Descriptive statistics will be provided for observed values as well as for change from baseline to all visits.

Another descriptive summary will be provided for the absolute change from pre-dose to post-dose values for the visits where pre- and post-dose values are assessed.

Individual subject changes

The number and percentage of subjects with at least one marked newly occurring or worsening abnormality for blood pressure will be summarized by period (Period 2, Period 3/ Safety follow-up [FU]) and overall (Period 2, 3, and FU combined) as shown in Table 7.

7.5.2 Physical findings

Physical examination will be conducted at screening, may be repeated at Visit 2 Day 1, and will be conducted at Visit 3.

The results of the physical examination will be listed. New abnormal physical findings will be reported as AEs.

7.5.3 WHO functional class

WHO FC (Class I–IV) as assessed by the investigator will be collected in the eCRF.

7.5.3.1 Measurements

WHO FC will be assessed at Screening Visit, Visit 2 Day 1, Visit 2 Day 3 (after the end of the last infusion), Visit 3, and at unscheduled visits.

7.5.3.2 Variables

For WHO FC, the following variables will be defined:

- Baseline value
- Value at each post-baseline visit
- Shift from baseline to each post-baseline visit
- Worst (highest) post-baseline value
- Best (lowest) post-baseline value.

7.5.3.3 Analysis

Values over time

A listing of all WHO FC assessments will be created displaying all values in the database, regardless if from scheduled or unscheduled visits.

Descriptive statistics (frequency tables) will be provided for observed values as well as for shift from baseline to all visits.

Individual subject changes

The worst/best post-baseline WHO FC will be displayed along with a shift table from baseline to worst/best post-baseline value.

7.6 Electrocardiograph

A standard 12-lead electrocardiograph (ECG) will be conducted on subjects in fully rested supine position. All ECG data from scheduled and unscheduled visits will be transferred to a central ECG laboratory. The ECG readouts (see below) will be transferred from the central ECG laboratory to trial data management and imported in the trial database.

7.6.1 Variables

The 12-lead ECG encompasses 3 categories of data obtained via the central ECG laboratory:

- Measurements:
 - ECG mean heart rate
 - PR interval,
 - QRS duration,
 - QT interval,
 - QTcB interval,
 - QTcF interval,
- Interpretation (normal/abnormal/unable to evaluate)
- Qualitative findings by category, as specified in the ECG data transfer specifications:

Table 11 Pre-specified ECG findings categories

Category
Atrioventricular Conduction
Axis and Voltage
Chamber Hypertrophy or Enlargement
Intraventricular-Intraatrial Conduction
Myocardial Infarction
Pacemaker
Sinus Node Rhythms and Arrhythmias
Supraventricular Arrhythmias
Supraventricular Tachyarrhythmias
ST Segment, T Wave and U wave
Ventricular Arrhythmias
Ventricular Tachyarrhythmias

ECG assessments will be performed at Visit 2 Day 1, Visit 2 Day 2 (pre-dose and 30 min after end of infusion for each of the two infusions), Visit 2 Day 3 (pre-dose and 30 min after end of infusion), Visit 3, and at unscheduled visits.

7.6.2 Variables

The following variables will be defined for the analysis of ECG parameters:

- Baseline values of quantitative ECG parameters
- Value at each post-baseline visit
- Absolute change from baseline to each post-baseline visit
- Absolute change from pre-dose after each infusion
- Proportion of qualitative ECG abnormalities

In addition, the incidence of QT prolongations is derived according to the criteria defined in [Table 12](#) below:

Table 12 QT prolongations in ECG parameters

Analysis Parameter	Analysis Variable(s)	Analysis Criterion
QTcB (msec)	Analysis value	- Value > 450
QTcF (msec)		- Value > 480 - Value > 500
	Change from baseline	- Increase from baseline > 30 - Increase from baseline > 60
	Analysis value and change from baseline	- Value > 450 and increase from baseline > 30 - Value > 450 and increase from baseline > 60

ECG = electrocardiograph; QTcB = QT interval corrected using Bazett's formula;
QTcF = QT interval corrected using Fridericia's formula.

7.6.3 Analysis

7.6.3.1 *Values over time*

A listing of all ECG measurements will be created displaying all values in the database. Abnormal ECG values will be flagged.

The overall interpretation and the findings will be presented in a separate listing.

For each parameter at each time over the course of the study, quantitative descriptive statistics for the value at the visit and the change from baseline will be presented by parameter and by time point.

Another descriptive summary will be provided for the absolute change from pre-dose to post-dose values in quantitative ECG parameters for the visits where pre- and post-dose values are assessed.

7.6.3.2 *Individual subject changes*

The number and percentage of subjects with at least one newly occurring or worsening abnormality for ECG parameters as defined in [Table 12](#) is provided by period as shown in [Table 7](#).

In addition, qualitative ECG findings will be tabulated by overall interpretation (normal, abnormal/unable to evaluate), and category [see [Table 11](#)].

7.7 Subgroup analysis of safety variables

In general, all safety variable summaries are presented by dose cohort as for study subject analyses [see Section 5].

No *a-priori* subgroup analyses are planned at this point.

7.8 Pharmacokinetic variables

7.8.1 Measurements

PK blood samples are collected at Visit 2 Day 1 (seven samples) and Visit 2 Day 3 (seven samples) to obtain 12-hour PK profiles of selexipag and its active metabolite, ACT-333679, at steady state for Uptravi and i.v. selexipag, respectively.

Endpoints derived during Period 1 are thus connected to Uptravi (Day 1) and endpoints during Period 2 are connected to i.v. selexipag (Day 3).

7.8.2 Pharmacokinetic endpoints

The following PK endpoints will be determined:

- $AUC_{\tau, ss}$ of selexipag and its active metabolite, ACT-333679, after Uptravi (oral selexipag) in Period 1 and after i.v. selexipag administration in Period 2.
- $C_{max, ss}$ of selexipag and its active metabolite, ACT-333679, after Uptravi (oral selexipag) in Period 1 and i.v. selexipag administration in Period 2.
- The time to reach maximum plasma concentration at steady state ($t_{max, ss}$) of selexipag and its active metabolite, ACT-333679, after Uptravi (oral selexipag) in Period 1 and i.v. selexipag administration in Period 2.
- Trough plasma concentration at steady state ($C_{trough, ss}$) of selexipag and its active metabolite, ACT-333679, after Uptravi (oral selexipag) in Period 1 and i.v. selexipag administration in Period 2.

7.8.3 Pharmacokinetic variables

Plasma PK parameters of selexipag and its active metabolite, ACT-333679, will be derived by non-compartmental analysis of the concentration-time profiles.

The PK parameters will be calculated on the basis of the real blood sampling time points (in relation to the last selexipag intake during each period).

The measured individual plasma concentrations of selexipag will be used to directly obtain $C_{trough, ss}$, $C_{max, ss}$, and $t_{max, ss}$.

$AUC_{\tau, ss}$ will be calculated according to the linear trapezoidal rule using the measured concentration-time values above the limit of quantification (LOQ) during one dosing interval at steady state.

7.8.3.1 Dose normalization

Dose normalization will be conducted to the lowest prescribed selexipag dose (200 µg for oral Uptravi and 225 µg for i.v. selexipag).

Dose normalized plasma concentrations, $C_{\text{trough, ss, norm}}$, $C_{\text{max, ss, norm}}$ and $AUC_{\tau, ss, \text{norm}}$ will be determined by dividing the respective parameters by the actual dose and multiplying with 200 or 225 for Uptravi and i.v. selexipag parameters, respectively.

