10.3.5 Analysis of PK variables

For all PK analyses, the Pharmacokinetic Analysis Set will be employed.

- Plasma concentrations of selexipag and ACT-333679 will be summarized per time point by dose and period using arithmetic mean, geometric mean, minimum, median,

maximum, standard deviation (SD), standard error (SE), and two-sided 95% CI of the means.

- $C_{trough, ss}$ of selexipag and ACT-333679 will be listed by dose, period and subject, and will be summarized by dose and period using arithmetic mean, geometric mean, minimum, median, maximum, SD, SE, and coefficients of variation (CV, CV_{ln}) in %, and two-sided 95% CI of the means.
- $C_{max, ss}$, $t_{max, ss}$, and $AUC_{\tau, ss}$ of selexipag and ACT-333679 will be listed by dose, period, and subject.
- $C_{max, ss}$, $t_{max, ss}^*$ and $AUC_{\tau, ss}$, will be summarized by dose and period with arithmetic mean, geometric mean, minimum, median, maximum, SD, SE, $CV\%$ and $CV_{ln}\%$, 95% CI of the arithmetic and geometric means, and inter-subject coefficient of variation (CV_b). (* For $t_{max, ss}$, the geometric mean, its 95% CI and CV_{ln} will not be calculated).
- Differences in $C_{max, ss}$ and $AUC_{\tau, ss}$ of selexipag and ACT-333679 between periods will be explored after dose normalization and within each dose level by using the 90% CI of the ratio of the geometric means of selexipag i.v. (test treatment) versus selexipag oral (reference treatment). The log-transformed values will be analyzed by mixed-effect models including treatment and period as fixed effects and subject as random effect. The ratios of geometric means and their 90% CI will be calculated from the corresponding back log-transformed contrasts of the mixed-effects models for $C_{max, ss}$ and $AUC_{\tau, ss}$ of selexipag and ACT-333679 after oral or i.v. selexipag administration.
- Differences for $t_{max, ss}$ of ACT-333679 between periods will be explored within each dose level using the Wilcoxon signed rank test providing the median differences and their 90% CI.
- Dose proportionality for $AUC_{\tau, ss}$ of selexipag and ACT-333679 after selexipag i.v. will be explored by the power model as described by [Gough 1995], (this analysis will only be done if there are at least 3 different doses in the study).
- $C_{max, ss}$ and $AUC_{\tau, ss}$ ratio of ACT-333679 / selexipag will be listed by dose, period, and subject and will be summarized by dose and period.

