3 OBJECTIVES

3.1 Primary objective

The primary objective of this study is to assess whether temporary switching from a stable oral dose of selexipag to an i.v. dose of selexipag providing comparable exposure (e.g., area under the plasma concentration-time curve during a dose interval at steady state [$AUC_{t, ss}$], maximum plasma concentration at steady state [$C_{max, ss}$]) to active metabolite ACT-333679 and switching back to the initial oral dose of selexipag is safe and well tolerated in subjects with stable PAH.

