7.8.4.2 Trough concentrations

Selexipag and ACT-333679 $C_{\text{trough, ss}}$ will be listed by dose, subject, and period as well as the ratio of the periods per subject.

Summary statistics will be provided by dose, including dose normalized, and by period. Implausible $C_{\text{trough, ss}}$ values will be flagged in the listings and not included in summary statistics.

7.8.4.3 $C_{\text{max, ss}}$, $t_{\text{max, ss}}$, and $AUC_{\tau, ss}$

$C_{\text{max, ss}}$, $t_{\text{max, ss}}$, and $AUC_{\tau, ss}$ of selexipag and ACT-333679 will be listed by dose, subject, and period. The ratio of the parameters between i.v. selexipag (test treatment) and Uptravi (reference treatment) per subject will be shown, except for $t_{\text{max, ss}}$. Any values

obtained from implausible plasma concentrations of selexipag or ACT-333679 will be flagged in the listings and not included in the statistical analysis.

Summary statistics will be provided by dose and period for selexipag and ACT-333679.

Dose-normalized $C_{max, ss}$ and $AUC_{\tau, ss}$ will be listed and summarized by period as well for selexipag and ACT-333679.

$C_{max, ss}$ and $AUC_{\tau, ss}$ ratio of ACT-333679/selexipag will be listed by dose, subject, and treatment and will be summarized by dose and treatment.

The ratio of $C_{max, ss}$ and $AUC_{\tau, ss}$ of selexipag and ACT-333679 between Uptravi and i.v. selexipag, after dose normalization, within each dose level (if sufficient subjects are enrolled per level) will be estimated by fitting a mixed effect model to the data using period (i.e., treatment) as fixed, and subject as random effect to the log-transformed $C_{max, ss}$ and $AUC_{\tau, ss}$ values. The ratios of geometric means between i.v. selexipag (test treatment) and Uptravi (reference treatment) will be computed and displayed together with their 90% CI by back-transforming the period contrasts and interval boundaries of the log-transformed data. If dose-proportionality is shown within each dose, then an overall model may be considered for robustness.

The inter-subject coefficient of variation (CV_b) of $C_{max, ss}$ and $AUC_{\tau, ss}$ of selexipag and ACT-333679 will be computed by using the mean squared error (MSE) of the mixed model as an estimate of variation.

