12.8 PK analyses

Output name	Display*	Title (Description)	Analysis set(s)**	Key deliverable	Mock layout
PK_CON_SUM_SEL	T	Summary of selexipag plasma concentrations [ng/mL] per time point by dose level and treatment	PKS		T_PK_CON_SUM

Output name	Display*	Title (Description)	Analysis set(s)**	Key deliverable	Mock layout
PK_CON_SUM_ACT	T	Summary of ACT-333679 plasma concentrations [ng/mL] per time point by dose level and treatment	PKS		T_PK_CON_SUM
PK_EP_SUM_SEL	T	Summary of PK endpoints of selexipag by dose level and treatment	PKS	Y	T_PK_EP_SUM
PK_EP_SUM_ACT	T	Summary of PK endpoints of ACT-333679 by dose level and treatment	PKS	Y	T_PK_EP_SUM
PK_SUM_RATIO	T	Summary of PK parameters of ratio ACT-333679/selexipag concentration by dose level and treatment	PKS		T_PK_RATIO_SUM
PK_MM_SEL	T	Mixed model analysis: Ratio of Uptravi and i.v. selexipag period for selexipag by dose level	PKS	Y	T_PK_MM
PK_MM_ACT	T	Mixed model analysis: Ratio of Uptravi and i.v. selexipag period for ACT-333679 by dose level	PKS	Y	T_PK_MM
PK_POW_AUC_SEL	T	Dose proportionality of AUCtau of selexipag after i.v. selexipag: Power model estimation	PKS	Y	T_PK_POW
PK_POW_AUC_SEL	F	Dose proportionality of AUCtau of selexipag after i.v. selexipag: Power model estimation	PKS	Y	F_PK_POW
PK_POW_AUC_ACT	T	Dose proportionality of AUCtau of ACT-333679 after i.v. selexipag: Power model estimation	PKS	Y	T_PK_POW
PK_POW_AUC_ACT	F	Dose proportionality of AUCtau of ACT-333679 after i.v. selexipag: Power model estimation	PKS	Y	F_PK_POW
PK_WIL_SEL	T	Location shift analysis of tmax, ss of selexipag	PKS		T_PK_WIL
PK_WIL_ACT	T	Location shift analysis of tmax, ss of ACT-333679	PKS		T_PK_WIL

* T=Summary table, L=Listing, F=Figure, **SCR=Screened analysis set, SAF=Safety analysis set, ivSAF=i.v. Safety analysis set, PKS=Pharmacokinetic analysis set

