Output: <Output name>, Produced by DATAMAP on ddMMMyyyy hh:mm (CET),

SDTM Date: ddMMMyyyy

Program: /<folder>/<program name>.sas

Page x of y

Programming note: Continue for dose all dose levels and dose normalized.

T PK RATIO SUM

ACT-293987

Protocol: AC-065A309

Summary of PK parameters of ratio ACT-333679/selexipag concentration by dose level and treatment Analysis Set: Pharmacokinetic Analysis Set

Dose level: 200 ug b.i.d. p.o./ 225 ug b.i.d. i.v.

PK parameter Statistic	Uptravi N=xxx	i.v. selexipag N=xxx
Subjects in dose level	xxx	xxx
AUCtau,ss [ng.h/mL]		
N	xxx	xxx
Arithmetic mean (95% CI)	xxx (xx.xx, xx.xx)	xxx (xx.xx, xx.xx)
Geometric mean (95% CI)	xxx (xx.xx, xx.xx)	xxx (xx.xx, xx.xx)
SD	xx.xxxx	xx.xxxx
SE	xx.xxxx	xx.xxxx
CV%	xx.xx	xx.xx
CV ln%	xx.xx	xx.xx
Median	xx.xx	xx.xx
Min, Max	xx.xx, xx.xx	xx.xx, xx.xx
Cmax,ss [ng/mL]		
n	xxx	xxx
Arithmetic mean (95% CI)	xxx (xx.xx, xx.xx)	xxx (xx.xx, xx.xx)
Geometric mean (95% CI)	xxx (xx.xx, xx.xx)	xxx (xx.xx, xx.xx)
SD	xx.xxxx	xx.xxxx
SE	xx.xxxx	xx.xxxx
CV%	xx.xx	xx.xx
CV ln%	xx.xx	xx.xx
Median	xx.xx	xx.xx
Min, Max	xx.xx, xx.xx	xx.xx, xx.xx

CI = Confidence interval, SD = Standard deviation, SE = Standard error, CV% = Coefficient of variation (SD/mean) [%], CV_ln% = Coefficient of variation of logarithmized values, [%] p.o. = per os, b.i.d. = twice daily; i.v.= intravenous

Values obtained from implausible plasma concentrations are not included in the summary.

Output: <Output name>, Produced by DATAMAP on ddMMMyyyy hh:mm (CET),

SDTM Date: ddMMMyyyy

Program: /<folder>/<program_name>.sas

Page x of y

Programming note: Continue for dose all dose levels and dose normalized.

T_PK_MM

ACT-293987

Protocol: AC-065A309

Mixed model analysis: Ratio of Uptravi and i.v. selexipag period for <selexipag/ACT-333679> by dose level

Analysis Set: Pharmacokinetic Analysis Set

Endpoint Statistic	Cmax,ss	AUCtau ss
Dose level: 200 ug b.i.d. p.o./ 225 ug b.i.d. i.v.		
n	xxx	xxx
Ratio of geom. means (i.v./p.o)	x.xx (x.xx, x.xx)	x.xx (x.xx, x.xx)
90% CI	x.xxxx, x.xxxx	x.xxxx, x.xxxx
CV b[%]	xx.xx	xx.xx
Dose level: 400 ug b.i.d. p.o./ 450 ug b.i.d. i.v.		
n	xxx	xxx
Ratio of geom. means (i.v./p.o)	xxx (xx.x, xx.x)	xxx (xx.x, xx.x)
90% CI	x.xxxx, x.xxxx	x.xxxx, x.xxxx
CV b[%]	xx.x	xx.x
Dose level: ...		
n	xxx	xxx
Ratio of geom. means (i.v./p.o)	xxx (xx.x, xx.x)	xxx (xx.x, xx.x)
90% CI	x.xxxx, x.xxxx	x.xxxx, x.xxxx
CV b[%]	xx.x	xx.x
...		
Dose level: Normalized dose (200 ug)		
n	xxx	xxx

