Ratio of geom. means (i.v./p.o)	xxx (xx.x, xx.x)	xxx (xx.x, xx.x)
90% CI	x.xxxx, x.xxxx	x.xxxx, x.xxxx
CV b[%]	xx.x	xx.x
CI = Confidence interval, n.e. = not estimable. p.o. = per os, b.i.d. = twice daily; i.v. = intravenous		
Geometric mean ratios were obtained by computing the anti-log of the treatment group difference of a mixed model with treatment as fixed and subject as random effect to the log-transformed data. CV_b[%] was computed using the mean squared error of residuals as a measure of variation. Values obtained from implausible plasma concentrations are not included in the analysis.		
Output: <Output name>, Produced by DATAMAP on ddMMMyyyy hh:mm (CET),		
SDTM Date: ddMMMyyyy		
Program: /<folder>/<program_name>.sas		
Page x of y		

Programming note: Display all dose levels. For dose levels not sufficiently populated to allow an estimation populate only 'n' row and show 'n.e.' for the remaining statistics.

T_PK_POW

ACT-293987

Protocol: AC-065A309

Dose proportionality of AUCtau of <selexipag/ACT-333679> after i.v. selexipag: Power model estimation

Analysis Set: Pharmacokinetic Analysis Set

n	beta	SE(beta)	90% CI
xxx	x.xxx	xx.xxxx	x.xxxx, x.xxx

CI = Confidence interval

Dose proportionality will be assumed if beta is close to 1, i.e., if the CI of beta includes 1.

Values obtained from implausible plasma concentrations are not included in the analysis.

Output: <Output name>, Produced by DATAMAP on ddMMMyyyy hh:mm (CET),

SDTM Date: ddMMMyyyy

Program: /<folder>/<program_name>.sas

Page x of y

Programming note: Produce table only if sufficient subjects are included in at least three dose levels.

T_PK_WIL

ACT-293987

Protocol: AC-065A309

Location shift analysis of tmax, ss of <selexipag/ACT-333679>

Analysis Set: Pharmacokinetic Analysis Set

n	i.v. selexipag - Uptravi Median	90% CI	p-value
xxx	x.xxx	x.xxxx, x.xxx	x.xxxx

CI = Confidence interval from a Hodges - Lehmann estimation.

p-value is derived from a Wilcoxon signed rank test.

Values obtained from implausible plasma concentrations are not included in the analysis.

Output: <Output name>, Produced by DATAMAP on ddMMMyyyy hh:mm (CET),

SDTM Date: ddMMMyyyy

Program: /<folder>/<program_name>.sas

Page x of y

[figure not shown]
F EXP

ACT-293987

Protocol: AC-065A309

Shift in selexipag dose between oral and i.v. treatment

Analysis Set: i.v. Safety Analysis Set

Output: <Output name>, Produced by DATAMAP on ddMMyyyy hh:mm (CET),

SDTM Date: ddMMyyyy

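### Is the dose-normalized i.v./oral exposure ratio defined on two different scales?

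*SAP*

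**What the plan says.** Protocol 10.3.5 says that differences in Cmax,ss and AUCτ,ss "between periods will be explored after dose normalization and within each dose level", using the geometric mean ratio of i.v. to oral with a 90% CI. It names no reference dose.

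SAP 7.8.3.1 supplies one. It normalizes to the lowest prescribed dose of each route, 200 µg oral and 225 µg i.v., by "dividing the respective parameters by the actual dose and multiplying with 200 or 225 for Uptravi and i.v. selexipag parameters, respectively". It also gives the normalized parameters their own variable names.

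SAP 7.8.4.3 and 8.2.2.1 fit the mixed model after dose normalization and do not restate the reference doses. On pooling across levels, 7.8.4.3 says: "If dose-proportionality is shown within each dose, then an overall model may be considered for robustness".

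SAP 12.8 lists the outputs, among them "Mixed model analysis: Ratio of Uptravi and i.v. selexipag period for ACT-333679 by dose level", which is marked as a key deliverable. In the mock layout, T_PK_MM, the individual rows name both doses, for example "Dose level: 200 ug b.i.d. p.o./ 225 ug b.i.d. i.v". The statistic is labelled "Ratio of geom. means (i.v./p.o" (closing parenthesis follows). The last row is headed "Dose level: Normalized dose (200 ug" and names the oral dose only.

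Protocol Table 1, repeated as SAP Table 6, pairs each oral dose with an i.v. dose. Protocol 5.1.1 says the pairing rests on study AC-065-110 and shows no calculation.

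**The concern.** Two normalizations are conceivable, and they estimate different things. Scaling oral to 200 µg and i.v. to 225 µg compares exposure at corresponding doses, which is the question the trial asks. Scaling both routes to 200 µg compares exposure per µg, a relative bioavailability. The SAP text describes the first, and the shell label can be read as the second.

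The row is not a trivial one. It is the only i.v./oral geometric mean ratio in the shells that pools dose levels, and many single levels will hold very few subjects. It therefore bears closely on the primary objective, which speaks of "temporary switching from a stable oral dose of selexipag to an i.v. dose of selexipag providing comparable exposure". Neither document sets a margin for comparable, so a reader will look at the printed ratio and at whether its interval covers 1. A constant factor of 1.125 could change that impression.

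The factor 1.125 is also built into the normalization, and its derivation from AC-065-110 is not shown.

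**Working it through.** **Inputs.** Paired doses: protocol Table 1. Normalization rule: SAP 7.8.3.1. AC-065-110 AUCs for ACT-333679, from protocol 1.2.4: 14.91 h·ng/mL (95% CI 11.42 to 19.47) after 200 µg i.v.; 37.97 h·ng/mL (30.18 to 47.78) after 400 µg oral; 18 healthy men.

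**Table 1 factor.** 225/200 = 450/400 = … = 1800/1600 = 1.125 in all eight rows.

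**The two readings.** Let D be the dose given.

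- SAP 7.8.3.1: (AUC_iv/D_iv × 225) / (AUC_po/D_po × 200). With D_iv/D_po = 1.125 this equals AUC_iv/AUC_po, the raw ratio at paired doses.
- Label taken literally: (AUC_iv/D_iv × 200) / (AUC_po/D_po × 200). With the same doses this equals (AUC_iv/AUC_po)/1.125.
- First divided by second: 225/200 = 1.125. This holds for any data and for both analytes, for AUC and Cmax, and for the estimate and both confidence limits.

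A raw ratio of 1.000 gives 1.000 and 0.889. A raw ratio of 1.125 gives 1.125 and 1.000.

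**Illustration with the printed AUCs.** The oral/i.v. metabolite AUC per µg is (37.97/400)/(14.91/200) = 1.273. At Table 1 doses the predicted i.v./oral ratio is 1.125/1.273 = 0.884 under the SAP rule and 1/1.273 = 0.785 under the literal label.

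The log-scale standard errors are ln(upper/lower)/(2 × 2.110) = 0.1264 (i.v.) and 0.1089 (oral). The SE of the difference is √(0.1264² + 0.1089² − 2ρ × 0.1264 × 0.1089), and the 90% CI is ratio × exp(±1.740 × SE) with 17 df. The correlation ρ is not in the documents, so it is shown as a range:

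| ρ (assumed) | SE | SAP rule | Literal label |
|---|---|---|---|
| 0 | 0.1669 | 0.66–1.18 | 0.59–1.05 |
| 0.5 | 0.1186 | 0.72–1.09 | 0.64–0.97 |
| 0.8 | 0.0763 | 0.77–1.01 | 0.69–0.90 |

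For ρ between about 0.31 and 0.83 the interval covers 1 under one reading and not under the other. This only restates the constant multiplier. It borrows single-dose variability in healthy men given a different i.v. formulation.

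**Which reading does the plan instruct?** Section 7.8.3.1 states the formula, both constants and the variable names. No section multiplies an i.v. parameter by 200. The individual rows of T_PK_MM are at paired doses, so a pooled row at the 200/225 level is on the same scale as they are; a per-µg row would not be. The SAP also habitually names dose groups by the oral dose: table columns are headed by Uptravi dose, and 5.5.1.3 converts i.v. doses to oral equivalents for display. Naming only 200 µg fits that shorthand.

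**Would a slip show?** Listing L_PK_DER prints each subject's i.v./oral ratio before and after normalization. With doses given as planned, the SAP rule makes the two equal. A 200/200 scaling would make every subject's normalized ratio smaller by the factor 1.125.

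**Subjects per level.** Overall 18/8 = 2.25. Group A enrols 5–8 over five levels (1.0–1.6 each). Group B enrols 12–15 over three levels (4–5 each), so the upper levels carry their own paired-dose ratios, whose labels are complete.

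**Derivation of 1.125.** The AC-065-110 point estimates give 1.273. An approximate 95% interval, 1.273 × exp(±√(0.2297² + 0.2668² − 2ρ × 0.2297 × 0.2668)), is 0.90–1.81 at ρ = 0, 0.99–1.64 at 0.5, 1.08–1.50 at 0.8 and 1.13–1.43 at 0.9. The value 1.125 lies inside for the first three and just outside at 0.9.

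**The case for a change.** The best argument for a change does not depend on a programming error. Even a correctly computed row would carry a heading that mentions only 200 µg above an i.v./oral ratio, and a reader could take it as bioavailability per µg. The heading also departs from the convention of the other rows in its own table. The output is a key deliverable and the correction is nearly free. On the factor, the protocol cites AC-065-110 but the AUCs it prints do not reproduce 1.125.

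Part of this stands. The heading is incomplete, and naming both doses would be better table-making. But that is finishing work on a mock-up, which SAP section 12 already allows for. It adds no instruction that 7.8.3.1 lacks. Repeating the reference doses in 8.2.2.1 would duplicate that section. Listing them in section 11.3 as a clarification is not needed either: protocol section 10 leaves derivation algorithms to the SAP, and the SAP supplies this one.

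The derivation point does not carry. Protocol 5.1.1 says the pairing was based on that study's results; it does not claim to be the quotient of two point estimates. Protocol 1.2.4 refers to the Investigator's Brochure, which is not available here. The gap is within uncertainty over most of the assumed range, and the SAP ratio is fully defined without the derivation. Nothing here bears on whether the factor or any dose is right.

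**Conclusion.** No change to the plan is needed. If the SAP is followed as written, the pooled row is the ratio at the paired doses of Table 1, on the same scale as the individual dose-level rows. The factor of 1.125 would appear only if someone set aside an explicit formula in favour of a parenthesis in a table shell, and the subject listing would reveal it. Protocol 10.3.1 and SAP 8.2 make the PK comparison descriptive, with no hypothesis test, and there is no margin, so no formal decision turns on whether the interval covers 1.

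What remains is a clerical slip in one row heading, with no effect on any estimate or interval. This conclusion assumes that the analysts program from section 7.8.3.1, which is the only definition they are given.
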